9.1.2. Baseline Visit

Baseline assessments will be performed pre-dose on Day 1. Since subjects will be transitioning from a previous migalastat study, the final visit of that study will be utilized to satisfy any duplicate Visit 1 (baseline) procedures required for the current study. The desired intent is for treatment with migalastat to continue without a break. However, any subject who did not receive migalastat for more than 30 days will be required to repeat all Visit 1 procedures.

All inclusion/exclusion criteria must be reviewed and verified at this visit to ensure that there have been no changes to a subject's health that would affect that subject's eligibility to participate in the study.

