10.1. Definitions

10.1.1. Adverse Event

An AE is defined as any untoward medical occurrence in a subject or clinical investigation subject administered a pharmaceutical product and which does not necessarily have a causal relationship with this treatment. An AE can therefore be any unfavorable and unintended sign, symptom, or disease temporally associated with the use of a medicinal product, whether or not considered related to the medicinal product.

Therefore, AEs include the following:

- The onset of new signs, symptoms, conditions, and illnesses
- Exacerbation of pre-existing conditions or illnesses
- Abnormal laboratory findings deemed clinically significant by the investigator
- Physical examination changes deemed clinically significant by the investigator
- Abnormal medical evaluation findings (eg, ECG) that are not documented at baseline and/or, in the investigator's opinion, represent a clinically significant change in the subject's health during study participation
 - Baseline medical evaluation findings (eg, ECG) that were not previously provided as medical history and can be determined as starting before baseline, are not considered AEs and will be recorded as medical history.

Adverse events will be recorded in the eCRF and subject's source record beginning from the time written consent (assent) is provided through the follow-up visit (at least 30 days after the last dose of study drug).

Subjects will be enrolling in this study following completion of Study AT1001-020. Therefore:

- Adverse events that are ongoing as of the last study visit of Study AT1001-020 will be entered in the AE eCRF.
 - The start date recorded in Study AT1001-020 will be the start date entered in the current study AE eCRF.
 - The event will be noted as continuing from Study AT1001-020 in the current study's AE eCRF.

A single diagnosis should be entered when known. If a clear diagnosis cannot be determined at the time of eCRF completion and the subject's source record entry, each sign and symptom must be recorded individually, until a final diagnosis is established. Conditions, signs, symptoms, etc that are present in the subjects' medical history at baseline should only be reported as AEs if they worsen (ie, increase in severity) since baseline.
Adverse events that begin after the first dose of investigational product in Study AT1001-036 will be considered treatment-emergent adverse events (TEAEs).

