5.6.1.2. Study Day

Study Day 1 denotes the day of the first dose of study drug in Study AT1001-036 and is the reference start date for all analyses in this study. Study days (or visit days) are defined relative to Day 1 unless otherwise specified. Days prior to Day 1 are negative and days after Day 1 are positive. There is no Day 0. That is,

Relative Day = (Date of Assessment) – (Date of First Dose of Study Drug) + 1, if assessment is on or after the date of first dose of study drug;

Relative Day = (Date of Assessment) – (Date of First Dose of Study Drug), if assessment is before the date of first dose of study drug.

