9.2. Adverse Events

A TEAE is defined as any untoward medical occurrence in a subject or clinical investigation subject administered a pharmaceutical product and which does not necessarily have a causal relationship with this treatment and that begins on or after the date of the first dose of study drug in the 036 study.

Treatment-related TEAEs are defined as TEAEs that have an Investigator-defined relationship to treatment of "Definite", "Probable" or "Possible". Events with an investigator-defined relationship of "Unrelated" or "Unlikely Related" are considered as not related to treatment.

Serious TEAEs are defined as TEAEs that have a "yes" response to the eCRF question "Event Serious?". Serious adverse events are categorized as "Death", "Life-threatening", "Requires/Prolongs Hospitalization", "Disability/ Incapacity", "Congenital Anomaly/Birth Defect" or "Important Medical Event or Reaction".

An overall summary of TEAEs, will be tabulated, including the number and percentage of subjects reporting, by sex and overall:

- TEAEs
- Treatment-related TEAEs
- SAEs
- TEAEs leading to discontinuation of study drug
- TEAEs leading to death

The number of events and incidence rates will also be provided in the overall summary table. Incidence rate is calculated as: total events divided by the total patient years of exposure. Total patient years of exposure are the sum of the duration of exposure in years for all subjects.

Further, the following TEAE summaries will be provided by sex and overall:

- Any TEAEs by SOC and PT
- Any TEAEs by PT
- Treatment-related TEAEs by SOC and PT
- TEAEs by severity, by SOC and PT
- Serious TEAEs by SOC and PT
- Any non-serious TEAE by PT

When presenting summaries by SOC and PT, subjects are counted only once within each SOC and PT. TEAEs will be presented alphabetically by SOC and PT.

When presenting summaries by PT, subjects are counted only once in each PT. TEAEs will be presented in the order of descending frequency in the overall group.

When presenting summaries by severity, if a subject has more than one event within a given SOC or PT at different severities, the maximum severity will be tabulated. For example, if a subject had two events with the same PT, but one was moderate and the other severe, the severe TEAE will be included in the tabulation.

Subject listings will be provided for all AEs, TEAEs leading to discontinuation of study drug, TEAEs with an outcome of death, and SAEs.

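### The SAP's treatment-emergent rule is wider than the protocol's by the pre-dose part of the first-dose day, so an AE carried over from AT1001-020 can be counted as a TEAE of AT1001-036, and SAP section 12 does not declare the difference

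*SAP*

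**What the plan says.** The protocol ties treatment emergence to the dose itself. Section 10.1.1 states: "Adverse events that begin after the first dose of investigational product in Study AT1001-036 will be considered treatment-emergent adverse events (TEAEs". SAP 9.2 ties it to the calendar day, counting an AE that "begins on or after the date of the first dose of study drug in the 036 study". SAP section 12 declares one change from the protocol, the merging of the analysis populations, and says there are no others.

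The first-dose day has a particular role in this design:

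- SAP 5.6.1.2: "Study Day 1 denotes the day of the first dose of study drug in Study AT1001-036".
- Protocol 9.1.2: "Baseline assessments will be performed pre-dose on Day 1". For subjects coming from AT1001-020, "the final visit of that study will be utilized to satisfy any duplicate Visit 1 (baseline) procedures required for the current study".
- Protocol 7.1 asks that enrolment follow directly on completion of AT1001-020.
- Protocol 10.1.1 has AEs recorded "beginning from the time written consent (assent) is provided through the follow-up visit". For AEs still ongoing at the last AT1001-020 visit it adds: "The start date recorded in Study AT1001-020 will be the start date entered in the current study AE eCRF". Those events are also to be marked in the AE eCRF as continuing from AT1001-020.
- Protocol 10.1.1 also has an exception. Baseline evaluation findings not previously given as history that "can be determined as starting before baseline, are not considered AEs and will be recorded as medical history".

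**The concern.** Long-term safety is the only primary objective, and TEAE incidence is part of the first-listed safety endpoint (Protocol 11.1.1). The TEAE flag feeds the SAP 9.2 tables by system organ class and preferred term, severity, relationship and seriousness, as well as the event rates per patient-year.

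A date-level rule is usually harmless at the start of treatment. Here subjects arrive already taking migalastat, and their first AT1001-036 day may also be the last assessment day of the previous study. Laboratory tests, ECG, echocardiogram and physical examination are all scheduled for the baseline visit. An AE that began in AT1001-020 can then enter the AT1001-036 count. SAP 5.5 also allows a pre-dose measurement from that day to be the subject's baseline, so the same value could be both the reference for change and the source of a TEAE.

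**Working it through.** The plan gives no figure to reproduce. The check applies both rules to each kind of AE onset around the first AT1001-036 dose.

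| Case | Protocol 10.1.1 | SAP 9.2 with 5.7.1 |
|---|---|---|
| (a) Complete start date equal to the first-dose date, onset before the dose | Not a TEAE | TEAE |
| (b) Same date, onset after the dose | TEAE | TEAE |
| (c) AE dated at the AT1001-020 final visit, which falls before the first-dose date | Not a TEAE | Not a TEAE |
| (d) Carried-over AE with a complete, earlier start date | Not a TEAE | Not a TEAE |
| (e) Baseline finding sent to medical history under Protocol 10.1.1 | Not an AE | Not an AE |
| (f) Carried-over AE with the start day missing and month and year matching the first dose, or the month missing and the year matching | No imputation rule given | Start set to the first-dose date, so TEAE, unless a stop date before that dose pulls it back |

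With complete dates, the rules part only in case (a). For a carried-over AE to fall there, three conditions must all hold:

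1. The AT1001-020 final visit and the first AT1001-036 dose share a date.
2. The event is recorded as an AE and not as medical history.
3. Its start date is that date.

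The documents permit all three together. Protocol 9.1.2 places baseline assessments before the dose on Day 1 and lets the previous study's final visit serve as Visit 1. Protocol 9.2.2.2.1 requires clinically significant laboratory abnormalities to be captured as AEs. Protocol 10.1.1 keeps the AT1001-020 start date.

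Case (f) is a second route and does not need the shared visit. An AE ongoing at the last AT1001-020 visit must have begun by then, yet SAP 5.7.1 can move its partial start date onto the first-dose date.

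**Size.** Let k be the number of subjects whose only TEAE is such an event. The percentage with any TEAE then rises by 100 × k/N. Protocol 8.1 and 11.2 and SAP 3.3 give no N, so these values are assumptions. For k = 1:

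- N = 10: 100 × 1/10 = 10 points
- N = 20: 100 × 1/20 = 5 points
- N = 25: 100 × 1/25 = 4 points

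A subject who has another TEAE adds nothing to the any-TEAE percentage but still adds to the event count. The documents give no AE counts and no visit-to-dose gaps, so k cannot be estimated.

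**The case against.** The strongest reply is that a date-level rule is a reasonable way to apply the protocol text. The documents do not show that AE onset time is collected, and the SAP works in dates throughout. Where time is unknown, onset after the dose cannot be programmed literally, and including the whole day errs towards counting the event. The tables are descriptive, nothing is tested, and all AEs are listed with dates as collected, so a reader could find the first-dose-day events. This stands as a defence of the default. It does not cover events that the AE eCRF already marks as continuing from AT1001-020, because no onset time is needed to recognise those. Nor does it explain why SAP section 12 is silent.

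A reader might go further and infer that findings at the shared visit become TEAEs as a matter of course. The documents do not support that. No section requires the AT1001-020 final visit to fall on the first-dose date. Dosing is every other day (Protocol 7.3.1), so the visit can fall on a day without a dose, and if it precedes the first-dose date both rules exclude its fully dated events. The medical-history exception in Protocol 10.1.1 removes some baseline findings. Protocol 9.2.2.6 limits recordable ECG findings to those absent before treatment started. Neither provision removes an AE already recorded in AT1001-020 and carried over.

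**Conclusion.** The definitions conflict and the SAP does not declare it. The SAP rule is wider by the pre-dose part of one calendar day per subject. Through that gap, or through the SAP 5.7.1 imputation, an AE that belongs to AT1001-020 can be counted as an AT1001-036 TEAE. AEs with a complete earlier start date and findings sent to medical history are unaffected.

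The effect is an over-count, probably small. It is 1/N for each subject with no other TEAE, and the N values shown are assumptions. A reader might want to attach an expected percentage of affected subjects, or to say that the serious and treatment-related rows are inflated. The documents contain nothing from which to derive either. The case for changing the text is that the error falls on the first-listed safety endpoint and the information needed to prevent it is already collected.

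**What to change.** Add a condition to SAP 9.2: an AE whose recorded or imputed start date is the first-dose date is a TEAE unless the AE eCRF notes it as continuing from AT1001-020, or its onset is known to precede the first AT1001-036 dose. If the timing is unknown and the event is not noted as continuing, count it as a TEAE. State that the condition is applied after the SAP 5.7.1 imputation, so that it also reaches partially dated carried-over events. Declare the date-based default in SAP section 12.

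This adds to the protocol rule and does not simply restate it, because Protocol 10.1.1 uses the continuing note only as a recording instruction. Exacerbations stay covered: Protocol 10.1.1 treats them as AEs, so a worsening after the first dose, entered with its own start date, would still count.

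The cost is one sentence in SAP 9.2, one condition in the TEAE flag and a line in section 12. No new data are needed for the continuing note.

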11.1. Endpoints

11.1.1. Safety Endpoints

Safety endpoints are as follows:

- incidence of TEAEs, SAEs, and AEs leading to discontinuation of study drug
- change from baseline in clinical laboratory test results over time
- change from baseline in vital signs over time
- change from baseline in physical examination findings over time
- change from baseline in body weight and height over time
- change from baseline in ECG results over time
- change from baseline in echocardiogram parameters over time
- change from baseline in Tanner Stage

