2.2.3. Safety Endpoints

The safety endpoints of this study are as follows:

- incidence of treatment-emergent adverse events (TEAEs), serious adverse events (SAEs), and adverse events (AEs) leading to discontinuation of study drug
- change from baseline in clinical laboratory test results over time
- change from baseline in vital signs over time
- change from baseline in physical examination findings over time
- change from baseline in body weight and height over time
- change from baseline in electrocardiogram (ECG) results over time

- change from baseline in echocardiogram (ECHO) parameters from baseline to Month 12/ET
- change from baseline in Tanner stage

3. Study Design

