8.1. Primary PD Endpoint and Analysis

The PD endpoint is change in plasma levels of lyso-Gb3. Descriptive summaries will be provided for the observed and change from baseline values to Month 6, and Month 12 by sex (male and female), ERT status (ERT naïve, ERT experienced), and overall based on the enrolled population.

A by-subject listing will also be provided.

9. Safety

The analysis population used for safety analyses will be the enrolled population. Safety will be assessed on the basis of extent of exposure, incidence of TEAEs, SAEs and AEs leading to discontinuation, clinical laboratory data, vital signs including body weight and height, ECG parameters, physical examinations, and Tanner stage.

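### The endpoint is AEs leading to discontinuation, but SAP 9.2 reports only TEAEs, so a non-serious AE carried over from AT1001-020 that ends treatment in 036 is in none of its tables

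*SAP*

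**What the plan says.** Protocol 11.1.1 defines the endpoint as "incidence of TEAEs, SAEs, and AEs leading to discontinuation of study drug". SAP 2.2.3 repeats it with "adverse events (AEs) leading to discontinuation of study drug", and the opening of SAP Section 9 says safety rests on, among other things, "incidence of TEAEs, SAEs and AEs leading to discontinuation". All three use TEAE for the first component and AE for the discontinuation component.

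SAP 9.2 then sets the analysis. A TEAE is an event "that begins on or after the date of the first dose of study drug in the 036 study". The overall table has a row for "TEAEs leading to discontinuation of study drug". The listings are given as: "Subject listings will be provided for all AEs, TEAEs leading to discontinuation of study drug, TEAEs with an outcome of death, and SAEs". For rates, "Incidence rate is calculated as: total events divided by the total patient years of exposure".

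Protocol 10.1.1 requires AEs still ongoing at the last AT1001-020 visit to be entered in the 036 AE form and marked as continuing from that study. On dating it says: "The start date recorded in Study AT1001-020 will be the start date entered in the current study AE eCRF".

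**The concern.** Endpoint and analysis cover different sets of events. The endpoint takes in any AE that makes a subject stop study drug. The analysis takes in only those that began in 036.

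The difference matters in a rollover study. Subjects arrive on continuous migalastat, and some will bring ongoing AEs with them. The intolerable-AE reason for stopping in Protocol 8.3.1 does not depend on when the event began, so an event that started in AT1001-020 can be why a subject stops in 036.

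The primary objective is long-term safety, and AEs leading to discontinuation are one of its stated endpoints. If SAP 9.2 is followed exactly, the count can be too low, and a reader would have to find the missing event in the listing of all AEs.

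**Working it through.** The plan gives no figure to reproduce. The check traces one event through every AE display in SAP 9.2.

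**The event.** A non-serious AE, ongoing at the last AT1001-020 visit, with a complete start date before the first 036 dose, not re-recorded as a new exacerbation, that leads to stopping migalastat in 036. By Protocol 10.1.1 it is in the 036 AE data with its AT1001-020 start date. By the SAP 9.2 definition it is not a TEAE.

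**The trace.**

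| SAP 9.2 display | Number | Requires | Event included in |
|---|---|---|---|
| Overall table, TEAE rows (any, related, discontinuation, death) | 4 | TEAE | 0 |
| Overall table, SAE row | 1 | serious | 0 |
| Further summaries | 6 | TEAE | 0 |
| **All summaries** | **11** | | **0** |
| Listing of all AEs | 1 | any AE | 1 |
| Listings of TEAEs leading to discontinuation, TEAEs with fatal outcome, SAEs | 3 | TEAE or serious | 0 |
| **All listings** | **4** | | **1** |

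**Effect on the reported incidence.** Let N be the number enrolled and k the number of other subjects who stop because of an AE and are counted. The table reports k/N, and the endpoint as worded is (k + 1)/N. The shortfall is 1/N whatever k is. The documents give neither N nor k, so both are assumed.

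| N | k = 0 | k = 1 | k = 2 | Shortfall (points) |
|---|---|---|---|---|
| 10 | 0.0% vs 10.0% | 10.0% vs 20.0% | 20.0% vs 30.0% | 10.0 |
| 20 | 0.0% vs 5.0% | 5.0% vs 10.0% | 10.0% vs 15.0% | 5.0 |
| 30 | 0.0% vs 3.3% | 3.3% vs 6.7% | 6.7% vs 10.0% | 3.3 |

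The share of the true count that is missed is 1/(k + 1): 100%, 50% or 33% for k = 0, 1 or 2.

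**Why carried-over events should stay out of the rate.** The denominator is exposure in 036. For an assumed N of 10 to 30 and mean exposure of 1 to 2 years, total exposure runs from 10 × 1 = 10 to 30 × 2 = 60 patient-years. One event with AT1001-020 onset would add 100/10 = 10.0 to 100/60 = 1.7 events per 100 patient-years, although its onset fell outside that exposure.

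**The case against.** The case is narrow, and several rules make it narrower.

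- **Worsening.** Protocol 10.1.1 counts exacerbation of a pre-existing condition as an AE. Protocol 9.2.1 treats conditions with onset at least 90 days before Visit 1 as medical history, and 10.1.1 makes medical-history conditions reportable when they increase in severity. A worsened event may therefore get a 036 onset and be a TEAE. This stands in part: the protocol does not say whether a carried-over AE that worsens gets a new record, and an event that simply becomes intolerable without increasing in severity has no 036 onset.
- **Entry rules.** Protocol 7.1 does not admit subjects who left AT1001-020 for safety or efficacy reasons. Exclusion 5 in 8.2.2 bars unacceptable risk, and 9.1.2 has all criteria re-verified at Visit 1. These make the case less likely, not impossible.
- **Visible elsewhere.** The event is in the listing of all AEs, and SAP 6.1 tabulates early discontinuation by reason. That table shows no AE term and is worded mainly for leaving the study. Protocol 8.3.2 lets a subject stop study drug and remain in follow-up.
- **Serious or partly dated events.** A serious carried-over event may reach the SAE row, though the scope of that row is unclear within a table described as a TEAE summary. Under SAP 5.7.1, a carried-over AE with a partly missing start date in the month or year of the first 036 dose can be imputed to that dose date and become a TEAE. Inclusion would then depend on how complete the date is.
- **The protocol's own listing.** Protocol 11.4.4.2 also limits its discontinuation listing to TEAEs. This is correct, so the SAP listing follows the protocol. The protocol's tables by system organ class and preferred term are described for AEs, whereas SAP 9.2 makes them all TEAE tables. SAP Section 12 does not declare that narrowing.
- **Magnitude.** The percentages are 1/N and 1/(k + 1) for assumed values. They show what one missed subject costs and say nothing about how likely one is. This stands in full.

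**Conclusion.** The concern holds. A non-serious AE with a complete AT1001-020 start date that leads to stopping migalastat in 036 meets the endpoint as worded, yet is in 0 of 11 summaries and 1 of 4 listings in SAP 9.2. Each such subject lowers the reported incidence by 1/N: 10.0, 5.0 or 3.3 points for an assumed N of 10, 20 or 30. With no other AE discontinuation, the table would show none when the true count is one.

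The conclusion rests on the event being known to be non-serious, fully dated and not re-recorded as a new exacerbation. Its frequency is unknown and may be zero. The information is not lost from the database, but it is missing from the displays meant to report the endpoint.

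**What to change.** - **Table and listing.** In SAP 9.2, tabulate (number and percentage of subjects) and list all AEs leading to discontinuation of study drug during 036 regardless of onset, split into treatment-emergent and carried over from AT1001-020.
- **Identification.** Use the continuing-event notation that Protocol 10.1.1 already requires. If that is not a structured field, use a start date before the first 036 dose.
- **Rate.** Keep carried-over events out of the events-per-patient-year calculation.
- **Protocol.** Align the TEAE-only listing in 11.4.4.2, through a clarification memo or the next amendment (Protocol 14.1.8).

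Rewording the endpoint to TEAEs and declaring this in SAP Section 12 would also remove the mismatch, but such events would still be absent from the tables.

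The cost is a SAP revision with one added table row shown by the split, one derived flag and a wider listing. AE recording does not change. The reported count may rise slightly.

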10.4. Reporting Events

10.4.1. Reporting Adverse Events

Information regarding AEs is to be obtained by questioning or examining the subject and/or parents or legally-authorized representatives.

As noted in Section 10.1.1, AEs will be recorded in the eCRF and subject source record beginning from the time written consent (assent) is provided through the follow-up visit (at least 30 days after the last dose of study drug). Required information will be detailed in the eCRF Completion Guidelines.

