9.1. Extent of Exposure and Drug Compliance

The duration of study drug exposure (in both days and months) and the number of doses of study drug exposure will be summarized for the enrolled population.

Duration of Exposure = end date of last dosing administration – start date of first dosing administration + 1Average Dose QOD = [Total dose received/ (Duration of exposure + 1)] * 2.

Drug Compliance (%) = Average Dose QOD/Planned Dose QOD (ie, 150 mg)

Drug Compliance will be summarized using descriptive summaries. The number and percentage of subjects with Drug Compliance <80%, $\ge80\%$ will be summarized.

A detailed listing of exposure to study drug and drug compliance will be presented.

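### The TEAE rate counts events beyond the last dose but divides by time up to the last dose, so most event rates in the overall summary table can be modestly overstated

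*SAP*

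**What the plan says.** **Rate.** SAP 9.2 adds event counts and incidence rates to the overall TEAE summary table, which is presented by sex and overall. The rule is "Incidence rate is calculated as: total events divided by the total patient years of exposure", and the denominator is explained as "Total patient years of exposure are the sum of the duration of exposure in years for all subjects".

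**Denominator.** SAP 9.1 defines duration of exposure as "end date of last dosing administration – start date of first dosing administration", plus one day. No follow-up time is added.

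**Numerator.** SAP 9.2 treats as a TEAE any event "that begins on or after the date of the first dose of study drug in the 036 study". Protocol 10.1.1 likewise sets only a start: "Adverse events that begin after the first dose of investigational product in Study AT1001-036 will be considered treatment-emergent adverse events". Neither gives an end.

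**Collection.** Protocol 10.4.1 has adverse events recorded from consent "through the follow-up visit (at least 30 days after the last dose of study drug". Protocol 9.1.5 asks all subjects to complete that visit, including those who stop drug or withdraw, and Protocol Table 2 schedules adverse event collection at it with a window of 6 days after the target date.

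**The concern.** An event that starts in the follow-up period enters the numerator, but the days in which it could occur are not in the denominator. The two halves of the rate describe different periods.

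Elsewhere the plan does draw a line at the end of treatment. SAP 6.4 flags medications started after the last dose as post-treatment, and SAP 9.3 limits potentially clinically significant laboratory values to the period on migalastat. Adverse events have no comparable bound, which suggests an omission rather than a choice.

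Events in follow-up are plausible here. Protocol 7.1 has subjects who can obtain reimbursed product switch to it, and Protocol 8.3.1 lists that eligibility as a withdrawal reason. Such subjects may still be taking migalastat during follow-up, so their event rate could stay close to the on-treatment rate.

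At stake is the accuracy of a descriptive safety rate in a study whose primary objective is long-term safety. If mean exposure differs between the sexes, the overstatement differs between the columns of the table as well.

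**Working it through.** The documents state no event count, rate or mean exposure, so there is no plan figure to reproduce. The check is person-time arithmetic.

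**Inputs**
- D, mean days from first to last dose. Not given; Protocol 7.2 says treatment length will vary. Assumed range 90 to 900 days. The estimated dates in the protocol synopsis, fourth quarter 2019 to second quarter 2022, allow about 1,000 days at most.
- F, days from last dose to follow-up visit. 30 from Protocol 9.1.5; 36 if the 6-day window is used in full.
- r, event rate in follow-up relative to the on-treatment rate. Not given; r = 1 means a constant rate.

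**Formulas**
- Planned rate divided by matched-window rate (same events over D + F days): (D + F)/D = 1 + F/D.
- Planned rate divided by on-treatment rate: 1 + r × F/D.

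With r = 1 the two agree. With r = 0 the planned rate equals the on-treatment rate.

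| Mean exposure D (days) | F/D, F = 30 | F/D, F = 36 | r × F/D, F = 30, r = 0.5 |
|---|---|---|---|
| 90 | 33.3% | 40.0% | 16.7% |
| 180 | 16.7% | 20.0% | 8.3% |
| 360 | 8.3% | 10.0% | 4.2% |
| 540 | 5.6% | 6.7% | 2.8% |
| 720 | 4.2% | 5.0% | 2.1% |
| 900 | 3.3% | 4.0% | 1.7% |

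**Worked illustration** (assumed: 20 subjects, 3 events per patient-year throughout, F = 30, 365.25 days per year). Follow-up adds 20 × 30/365.25 = 1.64 patient-years in each case.
- All at 360 days: exposure 20 × 360/365.25 = 19.71 patient-years. Expected events 3 × (19.71 + 1.64) = 64.1. Planned rate 64.1/19.71 = 3.25, or +8.3%.
- All at 720 days: exposure 39.43 patient-years, 123.2 events. Planned rate 3.125, or +4.2%.
- Ten at 90 days and ten at 720 days (mean 405): exposure 22.18 patient-years, 71.5 events. Planned rate 3.222, or +7.4%, which is 30/405.

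The matched-window rate is 3.0 in all three. The mixed case shows that, in a pooled ratio, mean exposure sets the size; a few short stays do not bring in the 33% figure.

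**By sex** (assumed means of 180 and 720 days, equal true rates): 1.167/1.042 = 1.12, an apparent 12% difference produced only by the denominator.

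**The case against.** The mismatch itself is not answered anywhere in the documents, but several limits on it stand.

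- A reader might infer that every reported rate is too high. The documents do not support that. An event starting after the last dose can hardly cause the drug to be stopped, so exposure time is the right denominator for TEAEs leading to discontinuation. Any other row exceeds its on-treatment rate only if at least one of its events starts after the last dose, and sparse rows such as deaths may have none.
- A reader might take the 33% at three months as the typical size. It would need the whole cohort to average 90 days, whereas the schedule runs to Month 24 and then repeats.
- A reader might treat the rate as the headline result for the primary objective. The safety endpoint is incidence, and Protocol 11.4.4.2 plans subject counts, percentages and event counts, with no rate per patient-year. The SAP puts the rate in one overall table; the tables by system organ class, preferred term and severity do not use this denominator.
- There is no comparator and no testing, so no treatment contrast is biased. Protocol 5.3.2.2 gives patient-years for earlier studies but no event rate to compare with.
- SAP 5.7.4 imputes a missing last-dose date as the last dispensation date plus two days per dose dispensed. For a subject who stopped mid-supply this lengthens the denominator and works in the opposite direction.
- Closing the TEAE window at exactly 30 days after the last dose could exclude events that the protocol collects, because the visit may fall later. This is a sound reason to correct the rate alone and not the TEAE definition.

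**Conclusion.** The concern holds in a limited form. Applied as written, SAP 9.1 and 9.2 give a rate whose events can extend at least 30 days beyond its person-time. Apart from the discontinuation row, the rates in the overall TEAE summary table can be overstated relative to a matched-window rate by up to about F/D: about 8%, 4% and 3% at mean exposures of 360, 720 and 900 days.

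These figures assume 30 days of completed follow-up for everyone and a constant event rate. If the rate halves after stopping, the excess over the on-treatment rate is about 4% to 2% over the same range. Subjects without completed follow-up reduce it further. The excess is large only if mean exposure is a few months, and the documents do not settle that. Subject counts and percentages are not affected.

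**What to change.** In SAP 9.2, for the incidence rate only, adopt one of these and name it in the table footnote:

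1. Denominator: sum each subject's time from first dose to the end of adverse event collection (the follow-up visit, or last contact if earlier). Keep exposure time for the discontinuation row.
2. Denominator unchanged; numerator limited to events with onset on or before the last dose.

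Leave the TEAE definition, the subject counts and percentages, and the SAP 9.1 duration of exposure as they are. In the same sentence, state how days become years: 365.25 days against twelve 30-day months changes the rate by about 1.5% (365.25/360 = 1.0146), and SAP 9.2 does not say which applies.

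The cost is a sentence and a footnote. Reported rates become slightly lower. Option 1 includes off-drug time for subjects who truly stop, which dilutes the rate if few events occur then. Under option 2 the rate's numerator may be smaller than the event count shown beside it, so the footnote must say so.
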